6.1 Anticipated Toxicities

CONFIDENTIAL

This document is confidential. Do not disclose or use except as authorized.

Dosing interruptions are permitted in the case of medical / surgical events or logistical reasons not related to study therapy (e.g., elective surgery, unrelated medical events, patient vacation, and/or holidays). Subjects should be placed back on study therapy within 3 weeks of the scheduled interruption, unless otherwise discussed with the Sponsor. The reason for interruption should be documented in the patient's study record.

No dose reductions are allowed for pembrolizumab. For toxicities that are attributable to pembrolizumab, this drug should be held as directed.

6.2 Management of toxicities attributable to pembrolizumab

Adverse events (both non-serious and serious) associated with pembrolizumab exposure may represent an immunologic etiology. These adverse events may occur shortly after the first dose or several months after the last dose of treatment. Pembrolizumab must be withheld for drug-related toxicities and severe or life-threatening AEs as per Table 4 below.

Table 4: Dose modification guidelines for Pembrolizumab for drug-related adverse events

Toxicity	Hold Treatment For Grade	Timing for Restarting Treatment	Discontinue Subject
Diarrhea/Colitis	2-3	Toxicity resolves to Grade 0-1.	Toxicity does not resolve within 12 weeks of last dose or inability to reduce corticosteroid to 10 mg or less of prednisone or equivalent per day within 12 weeks.
	4	Permanently discontinue	Permanently discontinue
AST, ALT, or Increased Bilirubin	2	Toxicity resolves to Grade 0-1	Toxicity does not resolve within 12 weeks of last dose.
	3-4	Permanently discontinue (see exception below) ¹	Permanently discontinue
Type 1 diabetes mellitus (if new onset) or Hyperglycemia	T1DM or 3-4	Hold pembrolizumab for new onset Type 1 diabetes mellitus or Grade 3-4 hyperglycemia associated with evidence of beta cell failure.	Resume pembrolizumab when patients are clinically and metabolically stable.
Hypophysitis	2-3	Toxicity resolves to Grade 0-1	Toxicity does not resolve within 12 weeks of last dose or inability to reduce corticosteroid to 10 mg or

CONFIDENTIAL

This document is confidential. Do not disclose or use except as authorized.

Toxicity	Hold Treatment For Grade	Timing for Restarting Treatment	Discontinue Subject
			less of prednisone or equivalent per day within 12 weeks.
	4	Permanently discontinue	Permanently discontinue
Hyperthyroidism	3	Toxicity resolves to Grade 0-1	Toxicity does not resolve within 12 weeks of last dose or inability to reduce corticosteroid to 10 mg or less of prednisone or equivalent per day within 12 weeks.
	4	Permanently discontinue	Permanently discontinue
Hypothyroidism	2-4	Therapy with pembrolizumab can be continued while treatment for the thyroid disorder is instituted	Therapy with pembrolizumab can be continued while treatment for the thyroid disorder is instituted.
Infusion Reaction	3-4	Permanently discontinue	Permanently discontinue
Myocarditis	1-2	Toxicity resolves to 0	Toxicity does not resolve within 12 weeks of last dose or inability to reduce corticosteroid to 10 mg or less of prednisone or equivalent per day within 12 weeks.
	3-4	Permanently discontinue	Permanently discontinue
Pneumonitis	2	Toxicity resolves to Grade 0-1	Toxicity does not resolve within 12 weeks of last dose or inability to reduce corticosteroid to 10 mg or less of prednisone or equivalent per day within 12 weeks.
	3-4	Permanently discontinue	Permanently discontinue
Renal Failure or Nephritis	2	Toxicity resolves to Grade 0-1	Toxicity does not resolve within 12 weeks of last dose or inability to reduce corticosteroid to 10 mg or less of prednisone or equivalent per day within 12 weeks.
	3-4	Permanently discontinue	Permanently discontinue

CONFIDENTIAL

This document is confidential. Do not disclose or use except as authorized.

Toxicity	Hold Treatment For Grade	Timing for Restarting Treatment	Discontinue Subject
All Other Drug-Related Toxicity ²	3 or Severe	Toxicity resolves to Grade 0-1	Toxicity does not resolve within 12 weeks of last dose or inability to reduce corticosteroid to 10 mg or less of prednisone or equivalent per day within 12 weeks.
	4	Permanently discontinue	Permanently discontinue

Note: Permanently discontinue for any severe or Grade 3 drug-related AE that recurs or any life-threatening event.

¹ For patients with liver metastasis who begin treatment with Grade 2 AST or ALT, if AST or ALT increases by greater than or equal to 50% relative to baseline and lasts for at least 1 week then patients should be discontinued.

² Patients with intolerable or persistent Grade 2 drug-related AE may hold study medication at physician discretion. Permanently discontinue study drug for persistent Grade 2 adverse reactions for which treatment with study drug has been held, that do not recover to Grade 0-1 within 12 weeks of the last dose.

Supportive care for pembrolizumab toxicity, particularly suspected immune-mediated toxicity
Subjects should receive appropriate supportive care measures as deemed necessary by the treating investigator. Suggested supportive care measures for the management of adverse events with potential immunologic etiology are outlined in Section 6 and in greater detail in the ECI guidance document, which is available from the study PI upon request. Where appropriate, these guidelines include the use of oral or intravenous treatment with corticosteroids as well as additional anti-inflammatory agents if symptoms do not improve with administration of corticosteroids.

Note that several courses of steroid tapering may be necessary as symptoms may worsen when the steroid dose is decreased. For each disorder, attempts should be made to rule out other causes such as metastatic disease or bacterial or viral infection, which might require additional supportive care. The treatment guidelines are intended to be applied when the investigator determines the events to be related to pembrolizumab.

Note: if after the evaluation the event is determined not to be related, the investigator is instructed to follow the ECI reporting guidance (see Section 7) but does not need to follow the treatment guidance (as outlined in the ECI guidance document).

It may be necessary to perform conditional procedures such as bronchoscopy, endoscopy, or skin photography as part of evaluation of the event. Suggested conditional procedures, as appropriate, can be found in the ECI guidance document.

- **Pneumonitis:**

- For **Grade 2 events**, treat with systemic corticosteroids. When symptoms improve to Grade 1 or less, steroid taper should be started and continued over no less than 4 weeks.

- For **Grade 3-4 events**, immediately treat with intravenous steroids. Administer additional anti-inflammatory measures, as needed.

- Add prophylactic antibiotics for opportunistic infections in the case of prolonged steroid administration.

- **Diarrhea/Colitis:**

Subjects should be carefully monitored for signs and symptoms of enterocolitis (such as diarrhea, abdominal pain, blood or mucus in stool, with or without fever) and of bowel perforation (such as peritoneal signs and ileus).

- All subjects who experience diarrhea/colitis should be advised to drink liberal quantities of clear fluids. If sufficient oral fluid intake is not feasible, fluid and electrolytes should be substituted via IV infusion. For Grade 2 or higher diarrhea, consider GI consultation and endoscopy to confirm or rule out colitis.

- For **Grade 2 diarrhea/colitis** that persists greater than 3 days, administer oral corticosteroids.

- For **Grade 3 or 4 diarrhea/colitis** that persists > 1 week, treat with intravenous steroids followed by high dose oral steroids.

- When symptoms improve to Grade 1 or less, steroid taper should be started and continued over no less than 4 weeks.

- **Type 1 diabetes mellitus (if new onset, including diabetic ketoacidosis [DKA]) or ≥ Grade 3 Hyperglycemia, if associated with ketosis (ketonuria) or metabolic acidosis (DKA)**

- **Hypophysitis:**

- For **Grade 2** events, treat with corticosteroids. When symptoms improve to Grade 1 or less, steroid taper should be started and continued over no less than 4 weeks. Replacement of appropriate hormones may be required as the steroid dose is tapered.

- For **Grade 3-4** events, treat with an initial dose of IV corticosteroids followed by oral corticosteroids. When symptoms improve to Grade 1 or less, steroid taper should be started and continued over no less than 4 weeks. Replacement of appropriate hormones may be required as the steroid dose is tapered.

- **Hyperthyroidism or Hypothyroidism:**

Thyroid disorders can occur at any time during treatment. Monitor patients for changes in thyroid function (at the start of treatment, periodically during treatment, and as indicated based on clinical evaluation) and for clinical signs and symptoms of thyroid disorders.

- **Grade 2** hyperthyroidism events (and **Grade 2-4** hypothyroidism):

- In hyperthyroidism, non-selective beta-blockers (e.g. propranolol) are suggested as initial therapy.

- In hypothyroidism, thyroid hormone replacement therapy, with levothyroxine or liothyroinine, is indicated per standard of care.

- **Grade 3-4** hyperthyroidism

- Treat with an initial dose of IV corticosteroid followed by oral corticosteroids. When symptoms improve to Grade 1 or less, steroid taper should be started and continued over no less than 4 weeks. Replacement of appropriate hormones may be required as the steroid dose is tapered.

- **Hepatic:**

- For **Grade 2** events, monitor liver function tests more frequently until returned to baseline values (consider weekly).
 - Treat with IV or oral corticosteroids
- For **Grade 3-4** events, treat with intravenous corticosteroids for 24 to 48 hours.
- When symptoms improve to Grade 1 or less, a steroid taper should be started and continued over no less than 4 weeks.

- **Renal Failure or Nephritis:**

- For **Grade 2** events, treat with corticosteroids.
- For **Grade 3-4** events, treat with systemic corticosteroids.
- When symptoms improve to Grade 1 or less, steroid taper should be started and continued over no less than 4 weeks.

- **Management of Infusion Reactions:** Signs and symptoms usually develop during or shortly after drug infusion and generally resolve completely within 24 hours of completion of infusion. Table 3 below shows treatment guidelines for subjects who experience an infusion reaction associated with administration of pembrolizumab.

Table 5: Infusion Reaction Treatment Guidelines for pembrolizumab

NCI CTCAE Grade	Treatment	Premedication at subsequent dosing
Grade 1 Mild reaction; infusion interruption not indicated; intervention not indicated	Increase monitoring of vital signs as medically indicated until the subject is deemed medically stable in the opinion of the investigator.	None
Grade 2 Requires infusion interruption but responds promptly to symptomatic treatment (e.g., antihistamines, NSAIDS, narcotics, IV fluids); prophylactic medications indicated for <=24 hrs	
Stop Infusion and monitor symptoms.
 
Additional appropriate medical therapy may include but is not limited to:
 
IV fluids Antihistamines NSAIDS Acetaminophen Narcotics
 
Increase monitoring of vital signs as medically indicated until the subject is deemed medically stable in the opinion of the investigator.
 
If symptoms resolve within one hour of stopping drug infusion, the infusion may be restarted at 50% of the original infusion rate (e.g., from 100 mL/hr to 50 mL/hr). Otherwise dosing will be held until symptoms resolve and the subject should be premedicated for the next scheduled dose.
 
Subjects who develop Grade 2 toxicity despite adequate premedication should be permanently discontinued from further trial treatment administration.
	
Subject may be premedicated 1.5h (\pm 30 minutes) prior to infusion of pembrolizumab with:
 
Diphenhydramine 50 mg po (or equivalent dose of antihistamine).
 
Acetaminophen 500-1000 mg po (or equivalent dose of antipyretic).

Grades 3 or 4 Grade 3: Prolonged (i.e., not rapidly responsive to	
Stop Infusion.
 
Additional appropriate medical therapy may include but is not limited to:
	No subsequent dosing

NCI CTCAE Grade	Treatment	Premedication at subsequent dosing
symptomatic medication and/or brief interruption of infusion); recurrence of symptoms following initial improvement; hospitalization indicated for other clinical sequelae (e.g., renal impairment, pulmonary infiltrates) Grade 4: Life-threatening; pressor or ventilatory support indicated	IV fluids Antihistamines NSAIDS Acetaminophen Narcotics Oxygen Pressors Corticosteroids Epinephrine Increase monitoring of vital signs as medically indicated until the subject is deemed medically stable in the opinion of the investigator. Hospitalization may be indicated. Subject is permanently discontinued from further trial treatment administration.	

Appropriate resuscitation equipment should be available in the room and a physician readily available during the period of drug administration.

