5.5 Definition of Dose-Limiting Toxicity

Pembrolizumab and radiation have been evaluated previously specifically in patients with SCCHN. However, although this is not a phase I protocol, the use of pembrolizumab in combination with high and low dose radiation is relatively novel, and therefore we plan to include a safety-run-in to ensure that treatment is well tolerated in this setting.

Dose-limiting toxicity (DLT) is based on the CTEP Active Version of the NCI Common Terminology Criteria for Adverse Events (CTCAE). DLT refers to toxicities experienced between the start of treatment and cycle 3, day 1 of pembrolizumab (the DLT evaluation period). A DLT will be defined as follows:

DLTs will be graded according to the National Cancer Institute's CTCAE v4.0 (<http://ctep.cancer.gov/forms/CTCAEv4.pdf>). A DLT is any event that: a) occurs during the DLT evaluation period; and b) is possibly, probably, or definitely related to the administration of pembrolizumab and radiation; and c) fulfills any of the following criteria:

1. Any Grade ≥ 3 pneumonitis, neurological event or uveitis.
2. Any Grade 2 pneumonitis, neurological event or uveitis, with the *following exception*:
 - Grade 2 pneumonitis, neurological event or uveitis that downgrade to Grade ≤ 1 within 3 days after onset, whereby maximal supportive care, including systemic corticosteroids, is permitted.
3. Any *other* Grade ≥ 3 toxicity, with the *following exceptions*:
 - Grade 3 irAEs that downgrade to Grade ≤ 2 within 3 days, or to Grade ≤ 1 or baseline within 14 days after onset, whereby maximal supportive care, including systemic corticosteroids, is permitted.
 - Grade 3 colitis that downgrades to Grade ≤ 2 within 7 days after onset, whereby maximal supportive care, including systemic corticosteroids, is permitted.

CONFIDENTIAL

This document is confidential. Do not disclose or use except as authorized.

- Grade 3 asymptomatic endocrinopathy, managed with or without systemic corticosteroid therapy and/or hormone replacement therapy.
- Grade 3 inflammatory reaction attributed to a local antitumor response (e.g., inflammatory reaction at sites of metastatic disease, lymph nodes, etc.).
- Grade 3 fatigue for \leq 7 days.
- Grade 3 infusion-related reaction (first occurrence and in the absence of steroid prophylaxis) that resolves within 6 hours with appropriate clinical management.

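### Section 6.2 starts steroids later for Grade 3-4 diarrhea/colitis (after more than 1 week) than for Grade 2 (after more than 3 days)

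*Combined protocol and SAP*

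**What the plan says.** The supportive-care list in section 6.2 has two adjacent bullets on when to start steroids for diarrhea/colitis:

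- Grade 2: an event "that persists greater than 3 days, administer oral corticosteroids".
- Grade 3 or 4: an event "that persists > 1 week, treat with intravenous steroids followed by high dose oral steroids".

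Other entries in the list give Grade 3-4 steroid instructions with no waiting period. For pneumonitis the instruction is to "immediately treat with intravenous steroids". The hypophysitis entry reads "events, treat with an initial dose of IV corticosteroids followed by oral corticosteroids", and the hepatic entry reads "events, treat with intravenous corticosteroids for 24 to 48 hours" (a treatment duration, not a wait).

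On the standing of the list, 6.2 says: "Suggested supportive care measures for the management of adverse events with potential immunologic etiology are outlined in Section 6". It adds that more detail is in a separate guidance document on events of clinical interest (ECIs), available on request and not part of this package.

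Table 4 holds pembrolizumab for Grade 2-3 diarrhea/colitis and stops it permanently at Grade 4. It does not say when steroids start.

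Section 5.5 has two exemptions that bear on a Grade 3 event. Colitis is not a DLT if it falls to Grade 2 or less "within 7 days after onset, whereby maximal supportive care, including systemic corticosteroids, is permitted". Any immune-related event is exempt if it falls to Grade 2 or less within 3 days, or to Grade 1 or less "or baseline within 14 days after onset, whereby maximal supportive care, including systemic corticosteroids, is permitted".

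**The concern.** The steroid trigger runs against severity. The Grade 2 bullet covers Grade 2 only, so from day 4 to day 7 a Grade 3 or 4 patient falls under the later rule alone. Read literally, a patient who worsens from Grade 2 to Grade 3 at about day 4 moves from treatment to waiting.

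What is at stake is patient safety. A site that follows the bullet as written delays steroids in its sickest colitis patients beyond the point at which it would treat milder disease. The same part of 6.2 tells sites to watch for bowel perforation, and Table 4 treats Grade 4 as reason to stop the drug for good. A week's wait at that grade does not fit with either.

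There is a lesser side effect. Section 5.5 allows for steroids within the 7 days after onset of Grade 3 colitis, but a start after more than 1 week comes too late to help an event meet that exemption.

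**Working it through.** The plan states no figure to reproduce here. The check is a comparison of the steroid rule by grade for each toxicity in 6.2, followed by short arithmetic.

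**Steroid start by grade, section 6.2**

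| Toxicity | Grade 2 | Grade 3-4 | Longer wait at the higher grade? |
|---|---|---|---|
| Diarrhea/colitis | after more than 3 days | after more than 1 week | Yes |
| Pneumonitis | no wait stated | immediate | No |
| Hypophysitis | no wait stated | no wait stated | No |
| Hyperthyroidism | beta-blockers, no steroids | no wait stated | No |
| Hepatic | no wait stated | no wait stated | No |
| Renal failure/nephritis | no wait stated | no wait stated | No |

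Other toxicities with a stated wait at Grade 3-4: 0 of 5. Infusion reactions (Table 5) list corticosteroids among the options at Grade 3-4, also without a wait. The diabetes/hyperglycemia bullet has no steroid instruction, and myocarditis appears only in Table 4.

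**Size of the inversion**

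- 1 week = 7 days, so the gap between triggers is 7 − 3 = 4 days.

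**Relation to the windows in 5.5, for a steroid start after day 7**

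- Colitis exemption: 7 − 7 = 0 days left.
- Immune-related exemption with the 14-day limit: at most 14 − 7 = 7 days left.
- A Grade 3 event may still meet the 14-day limit, or resolve within 7 days without steroids. Every event remains classifiable.

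**How many patients**

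The protocol gives no colitis rate for this combination. As an assumption, take the 60-patient head and neck monotherapy cohort in section 2.1.1.2, with 1 diarrhea event, grade not stated. Section 13.2 gives a maximum of 26 patients.

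- Rate: 1/60 = 1.7%.
- Exact 95% lower limit: 1 − 0.975^(1/60) = 0.00042, or 0.04%.
- Exact 95% upper limit: the p that solves (1 − p)^60 + 60p(1 − p)^59 = 0.025, which is 0.089, or 8.9%.
- Expected events of any grade: 26 × 1/60 = 0.43, with a range of 0.011 to 2.32 over those limits.

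The affected group is Grade 3-4 events that last more than 3 days, a subset of these. The figures therefore overstate its size if the assumed rate applies.

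**The case against.** The best case on the other side is that the bullet does not forbid earlier treatment and the protocol allows it in several places. Section 6.2 leaves supportive care to the treating investigator's judgment. Section 5.6.1 permits treatment the investigator considers necessary, and its steroid prohibition exempts ECIs of suspected immune origin; Appendix B lists diarrhea and colitis as ECIs from Grade 2. Section 5.5 permits steroids in the first 7 days of Grade 3 colitis. Other safeguards act before a week has passed: monitoring, fluids, consideration of GI consultation and endoscopy from Grade 2, the drug hold in Table 4, and ECI reporting to the sponsor within 24 hours under 7.8.5. The unseen guidance document may already give an earlier trigger. Diarrhea/colitis is also the only toxicity in 6.2 with a persistence threshold at any grade, so the comparison with the other five says little about ordering by grade.

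Much of this stands. It limits how far the bullet binds and how often it could matter, and the case rests mainly on the two bullets rather than on the 0-of-5 count. But none of it makes a longer wait for the sicker patient correct:

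- Suggested guidance exists to steer sites, and this trial provides for external ones (Appendix J).
- A document available on request cannot be assumed to cure the line.
- Work-up is to be considered from Grade 2, so it does not explain a longer wait at Grade 3-4 only.
- Holding the drug does not remove exposure quickly, given the half-life of about 4 weeks in section 2.1.1.2.

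A further objection is that matching the Grade 2 trigger would still allow a wait of more than 3 days at Grade 4. Setting the limit as no later than Grade 2 leaves the medical lead free to require immediate treatment.

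**Conclusion.** The concern holds. Section 6.2 as written makes Grade 3-4 diarrhea/colitis wait 4 days longer for steroids than Grade 2, and nothing else in the document restates or corrects the Grade 3-4 trigger. The line should be changed for patient safety.

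The practical reach is small. About 0.4 events of any grade are expected in 26 patients (0.01 to 2.3), on the assumption that the monotherapy diarrhea rate carries over to pembrolizumab with radiation. The effect at sites also depends on how literally they take suggested guidance and on what the separate ECI guidance says, neither of which can be judged from this document. The primary endpoint, sample size and stopping rules are not affected, and there is no defect in 5.5.

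**What to change.** Amend the Grade 3-4 diarrhea/colitis bullet in 6.2 so that its steroid trigger is no later than the Grade 2 trigger of more than 3 days. The medical lead should set the exact timing, which may be immediate, and check it against the ECI guidance document. Send sites a memo with the corrected line. Leave the DLT definition in 5.5 unchanged.

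The cost is one amended line and the memo.

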7. ADVERSE EVENTS: LIST AND REPORTING REQUIREMENTS

Adverse event (AE) monitoring and reporting is a routine part of every clinical trial. The following list of reported and/or potential AEs (Section 7.1) and the characteristics of an observed AE (Section 7.2) will determine whether the event requires expedited reporting **in addition** to routine reporting.

7.1 Adverse Events Lists

7.1.1 Adverse Event List(s) for pembrolizumab

Refer to the current version of Investigator's Brochure for detailed pembrolizumab safety/toxicity information.

7.1.2 Adverse Event List(s) for radiation

Adverse events for radiation are variable and depend on the site that is being irradiated. General side effects include fatigue, radiation dermatitis, and a low long term risk of a radiation induced malignancy. Other side effects include possible damage to normal tissues potentially included in the radiation treatment field (e.g. muscle, bone, nerve, mucosal surfaces, stomach, bowel, bladder, liver

CONFIDENTIAL

This document is confidential. Do not disclose or use except as authorized.

or heart). Doses to these normal structures are limited to the extent possible to minimize these risks as per section 5.4.

